### 9.1.1 Screening/Preoperative Visit (Visit 1)

Below are the procedures that will be done at the Screening/Preoperative visit.

NOTE: Any subject who signs an informed consent/assent but fails to meet the required entry

criteria is considered to be a consented Screen Failure.

1. Obtain written informed consent from the subject as detailed in **Section 7.5** 

### ----- Do not proceed until consent has been obtained -----

- 2. Obtain demographic information and medical history, including information on all concomitant medications/therapies.
- 3. Screen the subject for protocol inclusion/exclusion criteria.
- 4. Assign the subject a Subject ID.
- 5. Complete Screening and Enrollment Log.
- 6. Complete NOSE score assessment and VAS pain score.

This document contains information that is confidential and proprietary to Smith + Nephew PLC and Smith + Nephew, Inc. and is intended for use only by Smith + Nephew and its manufacturer. It shall not be reproduced or copied in whole or in part, nor shall the contents be disclosed by any means without prior written permission from Smith + Nephew, nor shall anyone make any use of it that is contrary to the expressed or implied wishes of Smith + Nephew.

Study Protocol	% smith&nephew
A prospective, multi-center, single arm PMCF study to evaluate	Number:
the safety and performance of ENTACT™ (Next Generation) resorbable septal staple system for septoplasty	ENTACT.ENT.PRO.SEP.2019.05
	Version: 2.0, 27Aug2020
	Page: Page 49 of 94

7. Subjects will be instructed to return for the Operation Visit (Procedure) as scheduled by the site.

## 9.1.2 Treatment/Operation Visit (Visit 2)

- 1. Query subject regarding any changes in general health and the use of concomitant medications.
- 2. Commence treatment/operation.
- 3. Confirm eligibility criteria
- 4. If any adverse device effects or device deficiencies are observed or reported, they must be recorded as instructed in **Section 12**, adverse events and device deficiencies. Also record concomitant medications/therapies used to treat AEs.
- 5. Record Intra-operative delivery success, total operation time and Intra-operative time for operative closure with ENTACT septal stapler.
- 6. Record device identification information for the stapler (e.g., Unique Device Identifier, Lot Number, Serial Number, Catalogue Number) and the number of staples used.
- 7. Instruct the subject on proper postoperative care/procedures, including any contraindicated treatments/medication(s).
- Instruct the subject on follow-up procedures, including returning the treatment facility in 5 days (± 2) days for follow-up visit.
- 9. Complete Operation and Discharge Visit CRFs.
- 10 If applicable, complete an End of Study CRF.

# 9.1.3 Follow-up Visit (Visit 3) Day 5 (± 2 days)

- Query subject regarding any changes in general health and the use of concomitant medications.
- 2. Record assessment of nasal cavity.

This document contains information that is confidential and proprietary to Smith + Nephew PLC and Smith + Nephew, Inc. and is intended for use only by Smith + Nephew and its manufacturer. It shall not be reproduced or copied in whole or in part, nor shall the contents be disclosed by any means without prior written permission from Smith + Nephew, nor shall anyone make any use of it that is contrary to the expressed or implied wishes of Smith + Nephew.

Study Protocol	> √ smith&nephew
A prospective, multi-center, single arm PMCF study to evaluate the safety and performance of ENTACT™ (Next Generation) resorbable septal staple system for septoplasty	Number: ENTACT.ENT.PRO.SEP.2019.05
	Version: 2.0, 27Aug2020
	Page: Page 50 of 94

- If any adverse device effects or device deficiencies are observed or reported, they must be recorded as instructed in Section 12, adverse events and device deficiencies. Also record concomitant medications/therapies used to treat AEs.
- 4. Complete NOSE score assessment and VAS pain score.
- 5. Instruct the subject on follow-up procedures, including returning the treatment facility at 21 days post-operative (± 7) days for follow-up visit.
- 6. If applicable, complete an End of Study CRF.

## 9.1.4 Follow-up Visit (Visit 4) Day 21 (± 7 days)

- 1. Query subject regarding any changes in general health and the use of concomitant medications.
- 2. Record assessment of nasal cavity.
- If any adverse device effects or device deficiencies are observed or reported, they must be recorded as instructed in Section 12, adverse events and device deficiencies. Also record concomitant medications/therapies used to treat AEs.
- 4. Complete NOSE score assessment and VAS pain score.
- 5. Instruct the subject on follow-up procedures, including returning the treatment facility at 42 days post-operative (± 7) days for follow-up visit.
- 6. If applicable, complete an End of Study CRF.

# 9.1.5 End if Study (Visit 5) Day 42 (± 7 days)

- 1. Query subject regarding any changes in general health and the use of concomitant medications.
- 2. Record assessment of nasal cavity.

This document contains information that is confidential and proprietary to Smith + Nephew PLC and Smith + Nephew, Inc. and is intended for use only by Smith + Nephew and its manufacturer. It shall not be reproduced or copied in whole or in part, nor shall the contents be disclosed by any means without prior written permission from Smith + Nephew, nor shall anyone make any use of it that is contrary to the expressed or implied wishes of Smith + Nephew.

Study Protocol	% smith&nephew
A prospective, multi-center, single arm PMCF study to evaluate	Number:
the safety and performance of ENTACT™ (Next Generation) resorbable septal staple system for septoplasty	ENTACT.ENT.PRO.SEP.2019.05
	Version: 2.0, 27Aug2020
	Page: Page 51 of 94

- 3. If any adverse device effects or device deficiencies are observed or reported, they must be recorded as instructed in **Section 12**, adverse events and device deficiencies. Also record concomitant medications/therapies used to treat AEs.
- 4. Complete NOSE score assessment and VAS pain score.
- 5. Complete an End of Study CRF.

Subjects may be provided participant stipends as agreed upon by Sponsor and the site, and as allowed by the site's standard operating procedures/regulations and IRB. Stipend amounts may cover costs associated with the study participant to complete follow-up visits, but cannot be coercive.

### 9.1.6 Concomitant Medications and Therapies

Concomitant medications and concomitant procedures are recorded at any time from enrollment into the study through the subject's last study visit.

Any concomitant medications/ procedures associated with an AE, SAE or SADE will be recorded.

### 9.1.7 Discontinued Subjects

Discontinued subjects are those who voluntarily discontinue participation, who are withdrawn for reasons of safety, who are lost to follow-up, or who have missed 2 study visits. Where possible, a full End of Study Visit should be completed for all subjects who discontinue the study early. Where consent is withdrawn, the date and any reason given for discontinuation should be captured, at a minimum (**see Section 7.9**).

Finally, if appropriate, the Investigator will also advise the subject of subsequent therapy and/or procedures necessary for their medical condition. Medical care will not be provided to the

This document contains information that is confidential and proprietary to Smith + Nephew PLC and Smith + Nephew, Inc. and is intended for use only by Smith + Nephew and its manufacturer. It shall not be reproduced or copied in whole or in part, nor shall the contents be disclosed by any means without prior written permission from Smith + Nephew, nor shall anyone make any use of it that is contrary to the expressed or implied wishes of Smith + Nephew.

Study Protocol	>∕smith&nephew
A prospective, multi-center, single arm PMCF study to evaluate the safety and performance of ENTACT™ (Next Generation) resorbable septal staple system for septoplasty	Number: ENTACT.ENT.PRO.SEP.2019.05
	Version: 2.0, 27Aug2020 Page: Page 52 of 94

subject after the clinical investigation is completed, other than the standard care provided by the site, which is not considered a study visit(s).

## 9.1.8 Subject Pregnancy

Women of child-bearing potential are not excluded from the study. However, if a woman becomes pregnant during the study, S+N must be contacted immediately once the investigator is made aware of the pregnancy and a decision will be made regarding the continuation in the study of the pregnant woman. Pregnancy is not an adverse event; however, complications related to the pregnancy may be reportable as determined on a case-by-case basis.

### 9.2 STUDY METHODS AND MEASUREMENTS

### 9.2.1 Nasal Obstruction Symptom Evaluation (NOSE) scale

The Nasal Obstruction Symptom Evaluation (NOSE) scale is a patient reported outcome (PRO) instrument that will be administered to capture subject perception of the degree of nasal airway patency. The Nose Scale will be completed at Screening, Day 5, Day 21 and Day 42.

The NOSE scale is a validated instrument, which was developed by the American Academy of Otolaryngology—Head and Neck Surgery (AAO-HNS), and has been used in several clinical trials. The scale is brief, easy to complete, and is an important tool for pre- and post-intervention evaluation of symptoms in subjects with nasal obstruction. The NOSE Scale allows subjects to quantify their symptoms based on the severity of obstruction.

Subjects will be asked, "Since your last follow up visit, how much of a problem were the following conditions for you?" Specifically, subjects will be asked to rate their perceptions on the Likert scale with respect to the following characteristics:

- Nasal congestion or stuffiness
- Nasal blockage or obstruction

This document contains information that is confidential and proprietary to Smith + Nephew PLC and Smith + Nephew, Inc. and is intended for use only by Smith + Nephew and its manufacturer. It shall not be reproduced or copied in whole or in part, nor shall the contents be disclosed by any means without prior written permission from Smith + Nephew, nor shall anyone make any use of it that is contrary to the expressed or implied wishes of Smith + Nephew.

Study Protocol	% smith&nephew
A prospective, multi-center, single arm PMCF study to evaluate the safety and performance of ENTACT™ (Next Generation) resorbable septal staple system for septoplasty	Number:
	Version: 2.0, 27Aug2020
	Page: Page 53 of 94

- Trouble breathing through my nose
- Trouble sleeping
- Unable to get enough air through my nose during exercise or exertion

Participants will rate their responses using a Likert scale with response options 0, 1, 2, 3 or 4, as follows:

- (0) Not a Problem
- (1) Very Mild Problem
- (2) Moderate Problem
- (3) Fairly Bad Problem
- (4) Severe Problem

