# **STUDY SCHEDULE**

Visit Type/name	Frequency / Time point
Screening/Pre-Operative (Visit 1)	(≤ 30 days) Within 30 days of Visit 2
Operative (Visit 2)	Day 0 - Surgery
Follow-up (Visit 3)	Day 5±2
Follow-up (Visit 4)	Day 21±7
End of Study (Visit 5)	Day 42±7

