### 9.2.2 Visual Analog Scale

A Visual Analog Scale (VAS) is a patient-reported outcome instrument that will be used to capture subjects' degree of pain and in the area where ENTACT resorbable staples were implanted. The Visual Analog Scale (VAS) for pain is a continuous scale completed by the subject who is asked to place a line perpendicular to the VAS line at the point that represents their pain intensity. Using a ruler, the score is determined by measuring the distance (mm) on the 10-cm line between the "no pain" anchor and the subject's mark, providing a range of scores from 0–100. For pain intensity, the scale is most commonly anchored by "no pain" (score of 0) and "pain as bad as it could be" or "worst imaginable pain" (score of 100 [100-mm scale]). The VAS will be completed at Screening, Day 5, Day 21, and Day 42.

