## 10.4.2 Analysis of Secondary Endpoints

Nasal cavity assessments at day 5 and day 42 will be summarized and presented as count and percentage of each criterion.

Successful staple deployment at the operative visit will be summarized by count and percentage. A 95% exact confidence interval for a single proportion will be presented for successful staple deployment using the Clopper-Pearson method. The number of staples used and whether the stapler misfired will also be presented.

Total operating room time will be calculated and summarized using descriptive statistics and will be presented descriptively by septoplasty only cases as well as septoplasty and turbinate reduction cases.

Intra-operative time to deploy staples to complete septoplasty, calculated as time between start of closure to when the stapler was handed back to the scrub nurse, will be summarized and presented descriptively by septoplasty only cases as well as septoplasty and turbinate reduction cases.

NOSE score will be calculated and summary statistics will be presented by visit. Change in NOSE score from the pre-operative visit to each post-operative visit will also be presented and an ANOVA model will be used to assess statistical significance.

This document contains information that is confidential and proprietary to Smith + Nephew PLC and Smith + Nephew, Inc. and is intended for use only by Smith + Nephew and its manufacturer. It shall not be reproduced or copied in whole or in part, nor shall the contents be disclosed by any means without prior written permission from Smith + Nephew, nor shall anyone make any use of it that is contrary to the expressed or implied wishes of Smith + Nephew.

Study Protocol	% smith&nephew
A prospective, multi-center, single arm PMCF study to evaluate the safety and performance of ENTACT™ (Next Generation) resorbable septal staple system for septoplasty	Number: ENTACT.ENT.PRO.SEP.2019.05
	Version: 2.0, 27Aug2020
	Page: Page 57 of 94

The VAS Pain score will be summarized by visit. Change in VAS Pain score from the preoperative visit to each post-operative visit will also be presented and an ANOVA model will be used to assess statistical significance.

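### The single NOSE question stem has no earlier visit to refer to at Screening, is ambiguous at Day 5, and covers varying periods at Days 21 and 42

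*Combined protocol and SAP*

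**What the plan says.** Section 9.2.1 says what subjects are to be asked: "Since your last follow up visit, how much of a problem were the following conditions for you". Five items follow, each scored 0 to 4. The same section sets the time points: "The Nose Scale will be completed at Screening, Day 5, Day 21 and Day 42". No other stem or recall period is given for any visit.

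The Study Schedule makes Screening Visit 1, "Within 30 days of Visit 2", where Visit 2 is the operation. The first visit labelled as follow-up is Visit 3, Day 5 ± 2. Visits 4 and 5 are at Day 21 ± 7 and Day 42 ± 7.

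NOSE and pain VAS at the pre-operative and all post-operative visits are secondary endpoints (section 8.3.2). For NOSE, section 10.4.2 states that change in "score from the pre-operative visit to each post-operative visit will also be presented", with an ANOVA model to assess significance. It plans the same for the VAS.

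Section 9.2.2 describes the VAS as measuring pain "in the area where ENTACT resorbable staples were implanted", and also schedules it at Screening: "The VAS will be completed at Screening, Day 5, Day 21, and Day 42". The subject's task, however, is described without a site: the subject is "asked to place a line perpendicular to the VAS line at the point that represents their pain intensity".

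**The concern.** A change score needs a baseline and a later value that measure the same thing over stated periods. Here the stem ties the period to an earlier follow-up visit. None exists at Screening, where the baseline is taken, and none exists at Day 5. At the later visits the period depends on how far apart the visits happened to fall.

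The study has no control arm, so within-subject change is the only contrast for this endpoint, and no comparator shares and cancels a recall effect. Nor can later analysis repair it: once a subject has answered, nothing in the data shows which period the subject had in mind. At stake is the interpretation of the tested NOSE change at three visits, most of all at Day 5, where one reading of the stem reaches back across surgery.

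**Working it through.** The plan states no look-back figure, so there is nothing to reproduce. The check takes the visit windows from the Study Schedule and works out which period the stem implies at each visit.

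Inputs, in days from surgery (Day 0):
- Screening: −30 to 0
- Day 5 visit: 5 − 2 = 3 to 5 + 2 = 7
- Day 21 visit: 21 − 7 = 14 to 21 + 7 = 28
- Day 42 visit: 42 − 7 = 35 to 42 + 7 = 49

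Formula: the shortest look-back is the earliest day of the current visit minus the latest day of the reference visit. The longest is the latest day of the current visit minus the earliest day of the reference visit.

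| Visit | Reference point | Shortest (days) | Longest (days) |
|---|---|---|---|
| Screening | none exists | – | – |
| Day 5, read as since surgery | Day 0 | 3 − 0 = 3 | 7 − 0 = 7 |
| Day 5, read as since Screening | Screening | 3 − 0 = 3 | 7 − (−30) = 37 |
| Day 21 | Day 5 visit | 14 − 7 = 7 | 28 − 3 = 25 |
| Day 42 | Day 21 visit | 35 − 28 = 7 | 49 − 14 = 35 |

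These ranges assume that no visit is missed. A single missed visit does not by itself make a subject lost to follow-up (section 7.8). A subject who misses Day 5 has no earlier follow-up visit at Day 21. One who misses Day 21 looks back at Day 42 over 35 − 7 = 28 to 49 − 3 = 46 days.

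Only the since-Screening reading at Day 5 crosses surgery when all visits are attended. If a subject reads the stem that way and symptoms have improved since the operation, the answer carries some pre-operative severity and the Day 5 change moves towards zero.

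For the fix, the shortest gap between consecutive follow-up visits is 7 days, both from Day 5 to Day 21 (14 − 7) and from Day 21 to Day 42 (35 − 28). A recall period of at most 7 days at those two visits therefore never reaches behind the preceding visit. At the earliest Day 21 visit it reaches back only to Day 14 − 7 = 7, which is after surgery.

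**The case against.** The case for leaving the text alone has several parts.

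- **The baseline exists.** A reader might infer that the NOSE baseline is undefined altogether. It is not: the visit, the five items and the response scale are all fixed, and a subject at Screening will still rate present or recent obstruction. What is missing is the recall period. This limits the point but does not remove it.
- **Day 5 has a natural reading.** The visit just before Day 5 is the operation, so many subjects will count from surgery, which is wholly post-operative. That is fair, and a bias at Day 5 cannot be asserted as certain. But the operation is not labelled a follow-up visit, and the text does not exclude counting from Screening.
- **The size is unknown.** A reader might combine the literature NOSE scores in section 4.2.1 (12 before, 2 after) with the look-back lengths to put a number on the Day 5 distortion. The documents do not support that. The score of 2 is a three-week result from 8 patients, and no Day 5 score is given anywhere. This objection stands in full.
- **The VAS is different.** A reader might infer that the VAS baseline fails in the same way, because no staple is in place at Screening. The staple-site phrase belongs to a garbled description of the instrument's purpose. The subject's task refers only to pain intensity, the area exists before surgery, and the VAS text contains no look-back. What remains is loose site wording.
- **The case report form may solve it.** The form is not in the documents and could carry a separate pre-operative stem. But section 9.2.1 states what subjects will be asked, so such a form would depart from the protocol and the two would still need reconciling.

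**Conclusion.** The point holds for the NOSE stem. As written, the prescribed question does not work at the visit that supplies the baseline, has two readings at Day 5 (3 to 7 days, or up to 37 days across surgery), and covers 7 to 25 days at Day 21 and 7 to 35 days at Day 42. This adds avoidable error to each tested change in NOSE. A pull towards zero at Day 5 follows only if subjects count back to Screening and their symptoms have improved; its size cannot be estimated from the documents.

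The conclusion assumes that the stem in section 9.2.1 is the one put to subjects, and the ranges assume that visits are attended within their windows. The VAS site wording is a minor matter. The effect is confined to secondary endpoints: the primary endpoint at Day 21 and the sample size of 36, raised to 40 for drop-out, do not depend on it. The change should be made, because it is cheap beforehand and cannot be made good afterwards.

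**What to change.** Before the first subject is enrolled, replace the stem in section 9.2.1 and on the case report form with wording that works at every visit and never spans surgery:

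- Screening: a stated, fixed recall period.
- Day 5: 'since your surgery'.
- Days 21 and 42: the same fixed period at both, at most 7 days, and preferably equal to the Screening period.

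Check the chosen wording against the instrument sources that the protocol cites (references 16 and 21) before adopting it. In section 9.2.2, describe the VAS site in words that also apply before surgery, for example pain in the nose, and use them at all visits.

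The cost is a wording change to section 9.2 and the form. Sections 21.1.1 and 21.1.3 say that enrolment starts under Version 2.0, so a change made before then affects no collected data. The downside is that the recall wording departs from the stem now drafted and may depart from the validated form of the instrument. The Day 5 period also remains 3 to 7 days because of the visit window, so it may still differ from the Screening period.

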### 9.2.2 Visual Analog Scale

A Visual Analog Scale (VAS) is a patient-reported outcome instrument that will be used to capture subjects' degree of pain and in the area where ENTACT resorbable staples were implanted. The Visual Analog Scale (VAS) for pain is a continuous scale completed by the subject who is asked to place a line perpendicular to the VAS line at the point that represents their pain intensity. Using a ruler, the score is determined by measuring the distance (mm) on the 10-cm line between the "no pain" anchor and the subject's mark, providing a range of scores from 0–100. For pain intensity, the scale is most commonly anchored by "no pain" (score of 0) and "pain as bad as it could be" or "worst imaginable pain" (score of 100 [100-mm scale]). The VAS will be completed at Screening, Day 5, Day 21, and Day 42.

## 10. STATISTICAL DESIGN

A Statistical Analysis Plan (SAP) will be written and finalized prior to database lock. The SAP will contain more specific details of the statistical analyses that will be carried out as well as provide information on any changes or deviations from the projected analyses in this protocol. The

This document contains information that is confidential and proprietary to Smith + Nephew PLC and Smith + Nephew, Inc. and is intended for use only by Smith + Nephew and its manufacturer. It shall not be reproduced or copied in whole or in part, nor shall the contents be disclosed by any means without prior written permission from Smith + Nephew, nor shall anyone make any use of it that is contrary to the expressed or implied wishes of Smith + Nephew.

Study Protocol	> ∕ smith&nephew
A prospective, multi-center, single arm PMCF study to evaluate the safety and performance of ENTACT ™ (Next Generation) resorbable septal staple system for septoplasty	Number: ENTACT.ENT.PRO.SEP.2019.05
	Version: 2.0, 27Aug2020
	Page: Page 54 of 94

Clinical Study Report (CSR) will also highlight changes made to the analyses specified in the protocol.

